7.2 Exclusion criteria

- Unwilling or unable to give informed consent
- Type 1 Diabetes Mellitus
- Other form of liver disease (other than NAFLD)
 - Viral hepatitis, Auto-immune hepatitis, primary sclerosing cholangitis, primary biliary cholangitis, haemochromatosis, Sarcoidosis, cystic fibrosis, sickle cell disease
- Taking medication associated with liver dysfunction (except methotrexate)
- Auto-immune disease which in the investigator's opinion may confound immune profiling
- Concomitant immunosuppressive medications (except methotrexate, short course oral steroids or inhaled corticosteroids)
- Currently pregnant
- Any major organ transplant (excluding corneal or hair transplant)
- Regular alcohol intake greater than 14 units a week for female participants and 21 units a week for male participants

8. Study design

This observational study will invite individuals from hospital outpatients (Gastroenterology and Bariatric services), community weight loss program or academic institutions associated with hospital sites to form the NAFLD and healthy control participants respectively. We plan to recruit 153 participants over an expected 24 month period. Opening this study at two bariatric surgery services we would expect to meet recruitment targets. However, if opportunistic recruitment does not meet expectations we will collaborate with other centres with whom we have existing relations (Imperial College and University College, London).

Participants will be approached at routine clinic appointments if pre-screened to meet study inclusion criteria. Community participants will have a short presentation at the beginning of their weight loss program where the study will be explained by one of

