At the first study visit a researcher will obtain informed consent and determine that the participant meets all study inclusion and exclusion criteria to proceed. Consent will include agreeing to access NHS databases for medical information and access to existing tissue samples surplus to clinical requirements. The study researcher will guide the participant through the consent form and case report form (CRF). This will also incorporate the Short Form (36) Health Survey (SF-36) as a measure of participant self-reported health status. This is in addition to medical and drug history in addition to smoking, alcohol, dietary and exercise data. The same assessment will take place at the final study visit, once they have achieved 5% to 7% weight loss.

Data collection will include:

1. History and examination: family history, smoking and drinking habits, past medical history, drug history, demographics (race, gender, age) and life-style (quality of life, dietary, exercise and sleeping habits).
2. Anthropometric measurement including body weight, body height, waist circumference and Body Mass Index (BMI).
3. Transient elastography (Fibroscan)
4. Fasted clinical blood tests including liver function and metabolic profile.
5. Fasted research blood tests - 55mls (3 tablespoons) extra.
6. Urine, saliva and stool samples
7. Optional fine needle aspiration of the liver

Every effort will be made to arrange all study procedures at each time point in a single visit, however, if this is not possible, participants have the option to return at an alternative date for that component / those components.

If a participant is undergoing bariatric or upper gastrointestinal surgery for a non-malignant indication, a study investigator or research nurse will attend the day of their surgery and collect the tissue samples: liver and adipose tissue and gut tissue (if their operation includes bowel resection) having consented previously. All participants with NAFLD will be offered a follow up visit once they have achieved 5% to 7% weight loss with repeat assessment of immune-profile and liver specific tests. Additional consent pertaining to fine needle liver aspirate will be obtained immediately prior to this procedure. The standard NHS consent form will be used for this.

Study procedures by visit

Study intervention	Visit 1	Visit 2 (Surgical & biopsy participants only)	Visit 3 (5%-7% weight loss achieved)
Informed Consent	X		
Screening	X		
Medical history	X	X	X

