Participants will have an optional fine needle aspiration of their liver at baseline and at follow up, once attaining 5% to 7% weight loss. This procedure has been in use for more than 20 years as a research and clinical tool with better safety profile than standard liver biopsy.³⁴ A recent study revealed safe repeated fine needle aspiration from the same study participants with the only adverse event reported as pain post procedure requiring simple analgesia in two cases after 39 fine needle aspirates.³⁵ Furthermore, another research group has reported no serious complications in a series of more than 500 fine needle liver aspirates.³⁶ In this study, liver FNA will be only undertaken by individuals with adequate prior experience to minimise risk to participants.

We expect small risk to study researchers undertaking analysis of biological samples from this study. Standard mitigating precautions including personal protective equipment, sealed containers opened only in fume hoods within containment level 2 laboratory facilities will be adhered to. Further information can be found in section 15 regarding laboratories. All research staff dealing with samples will have to demonstrate up to date safety training either from their employing NHS trust or academic institution.

11. Statistical considerations

Patients undergoing assessment for bariatric surgery will predominantly be classified as obese, BMI $>30\text{Kg/m}^2$ ($>27.5\text{Kg/m}^2$ for South Asian patients) or more likely severely obese, BMI greater than 35Kg/m^2 . It is recognised that up to 90% of obese individuals will have concurrent NAFLD.¹ A recent meta-analysis reports the incidence of NASH among NAFLD patients to be 59.1%⁴¹ although in a bariatric cohort with more risk factors, a higher proportion is expected. A previous NAFLD study in 109 predominantly Caucasian bariatric patients revealed that almost 90% of patients undergoing bariatric surgery had evidence of NASH with at least stage 1 (out of 4) fibrosis¹⁹.

In this exploratory, basic science observational project, formal power calculations are not possible. However similar work by our group suggests that 40 patients in each of the following groups: NASH with mild fibrosis (stages 0-1) and significant fibrosis (stages 2-4) will be informative. Given that we cannot determine the stage of disease before surgery, and assuming a conservative NASH rate of 75% of all patients and a

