relatively even split of patients into the two categories and 20 healthy control participants we estimate that a total sample size of 153 will enable us to recruit with 20% contingency for dropout.

Techniques involved in analysis of biological samples will include flow cytometry, quantitative polymerase chain reaction, RNA sequencing of immune cell populations, 16S ribosomal RNA sequencing of the microbiome and enzyme-linked immunosorbent assays on serum or plasma samples.

The data will be analysed using widely used statistical packages Graphpad Prism and Statistical Package for the Social Sciences (SPSS) utilising descriptive statistical tests. Specific techniques may require additional software such as CytoBank for CyTOF data and HistoCAT for imaging mass cytometry.

12. Ethics

The Principal Investigator must ensure that the study will be carried out in accordance with the ethical principles in the Research Governance Framework for Health and Social Care, Second Edition, 2005 and its subsequent amendments as applicable and applicable legal and regulatory requirements.

None of the Investigators declare any conflicts of interest with regards to this study.

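### Was the 20% dropout allowance behind the total of 153 multiplied on (x 1.2) when it should have been divided out (/ 0.8)?

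*Protocol*

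**What the plan says.** The sample size reasoning is in Protocol Section 11 (Statistical considerations). There is no formal power calculation. The total is built from target group sizes and an expected yield:

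- Target: "40 patients in each of the following groups: NASH with mild fibrosis (stages 0-1) and significant fibrosis (stages 2-4) will be informative".
- Yield: "assuming a conservative NASH rate of 75% of all patients", because the stage of disease is not known before surgery.
- Allocation: a "relatively even split of patients into the two categories".
- Controls: "20 healthy control participants".
- Total: "we estimate that a total sample size of 153 will enable us to recruit with 20% contingency for dropout".

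Section 8 (Study design) repeats the total: "We plan to recruit 153 participants over an expected 24 month period". The synopsis in Section 4 gives the same number. No section prints a figure before the dropout allowance, shows a multiplication or division, or says whether the allowance covers the controls. On follow-up, Section 9 (Study procedures) states: "All participants with NAFLD will be offered a follow up visit once they have achieved 5% to 7% weight loss".

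**The concern.** Allowing for dropout by multiplying the evaluable number by 1 + d, when it should be divided by 1 - d, is a common mistake in sample size sections. Here the multiplication lands on the printed total. The sentence attaches the allowance to the total and names the controls just before it, so inflating patients and controls together is a natural first reading.

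If that is how 153 arose, it tolerates a loss of 26/153 = 17.0%, less than the 20% named, and a loss of 20% leaves 122.4 participants against 127. With no power calculation, this yield arithmetic is the whole justification for 153. A slip would mean that the plan misses its own group targets even if every other assumption holds.

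**Working it through.** **Inputs, all from Section 11:** 40 + 40 = 80 NASH patients; NASH rate 0.75; 20 controls; dropout allowance 0.20.

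**Route A: patients and controls together, multiplied.**
- Patients before dropout: 80 / 0.75 = 106.67, rounded up to 107.
- With controls: 107 + 20 = 127.
- Inflated: 127 x 1.2 = 152.4, rounded up to 153.
- Without the first rounding: (106.67 + 20) x 1.2 = 152.0, which is not 153.

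**Route B: patients and controls together, divided.**
- 127 / 0.8 = 158.75, rounded up to 159. This does not reproduce the printed total.

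**Route C: patients only, divided, controls then added.**
- NASH patients to recruit: 80 / 0.8 = 100.
- Patients to recruit: 100 / 0.75 = 133.33.
- With controls: 133.33 + 20 = 153.33, which is 153 to the nearest whole number. Strict rounding up gives 134 + 20 = 154.

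**Route D: patients only, multiplied.**
- 80 x 1.2 / 0.75 + 20 = 128 + 20 = 148. This does not reproduce the printed total.

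So two routes reach 153: A, which contains the suspected slip, and C, which uses the correct N / (1 - d). Each depends on a rounding choice. A needs two roundings up, while C needs ordinary rounding of 153.33. Rounding therefore cannot show which route was used, and no printed intermediate figure (127 or 133) decides it.

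**Does 153 meet the targets on Route C?**
- Patients left after 20% dropout: 133 x 0.8 = 106.4.
- With NASH: 106.4 x 0.75 = 79.8, or 39.9 per fibrosis group against 40.
- Dropout that 133 patients tolerate: 1 - 106.67/133 = 19.8%.
- Controls: 20 recruited for 20 wanted.

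The remaining gap is 0.2 of a patient, which is rounding.

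**Is an allowance for patients only consistent with the protocol?** The primary objective in Section 6.1 concerns people with NAFLD who lose weight. Section 9 offers the weight-loss follow-up visit to participants with NAFLD. For controls, Section 8 places the eligibility scan at the screening visit, which is combined with the first study visit, and the visit table in Section 9 puts blood and other samples at that same visit. Later loss would therefore fall mainly on the patients, and an allowance confined to them is a reasonable design choice.

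**The case for a change.** The strongest counter-argument is that controls can also be lost. Section 8 gives controls who have elective abdominal surgery a second visit on the day of surgery, and says in general terms that every participant has a final visit. Section 9 lets any participant withdraw and have data and samples destroyed. If 20% of every group were lost, the Route C split would leave 106.4 patients and 20 x 0.8 = 16 controls, again 122.4 in total. On this view 153 falls short whichever route produced it, because the sentence ties the allowance to the total.

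The arithmetic is right, and some loss of controls is possible. But the conclusion needs a 20% loss among controls, and the protocol does not state one. The general remark about a final visit is conditional on 5% to 7% weight loss, with a six-month visit for those who do not reach it, which fits the NAFLD participants better than the controls. Leaving open whether the allowance covers controls makes the text unclear; it does not make the figure wrong.

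The wording also leaves room for Route A itself. The protocol speaks of a contingency of 20%, which can mean 20% extra recruits, and x 1.2 provides exactly that. On this reading too, the figure matches its description.

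**Conclusion.** The concern does not stand. It would hold only if 153 could come from nothing but 127 x 1.2, and it can also come from correct division over the patients with 20 controls added (153.3). On that route the plan keeps 79.8 of its 80 NASH patients at 20% dropout. The figures of 17% tolerance, 122 remaining against 127, and 159 required depend on two assumptions that the protocol does not make: that the allowance covers the controls, and that 20% is a loss rate applied to everyone recruited.

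Even on those assumptions the effect would be small: 6 participants in total (159 - 153). If the 153 are split as 129 patients and 24 controls (20 x 1.2), 129 x 0.8 x 0.75 / 2 = 38.7 remain per NASH group instead of 40, and 24 x 0.8 = 19.2 controls instead of 20. In an exploratory study with no stated power, alpha or effect size, that is minor beside the uncertainty in the 75% NASH rate and the assumed even split.

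Restating the plan as 17% tolerance or 122 evaluable participants could replace a correct figure with a wrong one. Showing the steps and saying to whom the 20% applies would make the section easier to read, but the absence of that detail is not an error in the number.

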12.1 Annual Safety Reporting

The CI will send an Annual Progress Report to the REC and the sponsor using the HRA template on the anniversary of the REC “favourable opinion”.

13. Public Involvement

The work of the group has been discussed with the North Thames Diabetes lay Panel and our results will be reported back to them at their quarterly meetings.

14. Data handling and record keeping

14.1 Data management

Data pertaining to study participants will be recorded directly recorded into CRF which in turn would be transcribed into an anonymised electronic excel database stored as per the conditions below.

- Confidentiality

Personal data will be stored in password-protected formats on hospital networks. We will follow local Trust guidelines on the storage and transfer of

data and all databases / spreadsheets will be compliant with the Data Protection Act, NHS Caldecott Principles, The Research Governance Framework for Health and Social Care, and the conditions of Research Ethics Committee Approval.

- Record Retention and Archiving

Data will be stored in codified, password-protected formats. We will follow local Trust guidelines on the storage and transfer of data and databases / spreadsheets will be Caldicott compliant. The UK Policy Framework for Health and Social Care Research requires that research records are kept for 20 years after the project has completed and will be archived in the Trust Corporate Records Centre.

14.2 Source data

Source data will include the CRF incorporating the questionnaires completed at time of first visit in addition to participant's hospital medical records, NHS databases and General Practitioner records (if consent given to access these). The total accumulated data will be collated in an anonymised electronic database.

14.3 Confidentiality

Information related to participants should be kept confidential and managed in accordance with the Data Protection Act, the General Data Protection Regulation (GDPR), NHS Caldecott Principles, the UK Policy Framework for Health and Social Care Research, and the conditions of Research Ethics Committee favourable opinion. Only data outlined in the protocol will be collected from study participants and anonymised within the study database. Only members of the research team will have access to healthcare records and source documents.

15. Laboratories

15.2 Sample collection and preparation

Research samples will be collected at all study sites pseudo-anonymised and labelled with the patient study number. Material transfer agreements will be arranged with each study site with regards to the transfer of participant samples. All sample processing will occur at the primary site run by the chief investigator.

15.3 Laboratory procedures

These may include flow cytometry, mass cytometry (CyTOF), imaging mass cytometry, tissue culture, nucleic acid and protein detection, mass spectrometry, bacterial sequencing and identification, metabolic profiling.

Working with human tissue products (blood, tumour tissue, urine, stool, saliva, plasma, serum) has inherent risks; tissue, whether screened or unscreened, can carry infectious agents and so will require careful handling.

All researchers planning to work with human tissue must ensure that they:

- Are trained in all necessary procedures.
- Are vaccinated against Hepatitis B.
- PPE (gloves, lab coat and eye protection) is worn.

Study personnel must:

- Avoid the use of sharps, but if unavoidable, follow safe sharps practice; if possible, no sharps should be used when handling blood samples that have been collected elsewhere.
- Where possible, process samples in a Safety Cabinet.
- Only work in designated areas
- All other work with samples should be carried out in at Containment Level 2

15.4 Sample storage and transfer

All human tissue/product samples must be separately transferred or stored in watertight plastic containers and labelled appropriately (contents, date collected, name of researcher and a biohazard label). The laboratory is equipped with a spill kits for infectious material.

The triple packaging system described by the WHO must be used for all infectious substances (Category A and B), exempt substances and non-infectious GM substances.

This consists of three layers as follows:

Primary receptacle: water-tight and leak proof with enough absorbent material to absorb all fluid in the event of a breakage.

Secondary receptacle: a durable, water-tight and leak-proof packaging to enclose and protect the primary receptacle. Several cushioned primary receptacles may be placed in one secondary package but sufficient absorbent material should be used to absorb all fluid in a breakage. Goods of an unrelated type must not be packed together.

Outer packaging: secondary receptacles are placed in a durable outer packaging with suitable cushioning material to protect from outside influences.

Samples will be stored in either minus 80 freeze or liquid nitrogen storage to minimise degradation of participant samples. Only laboratory personnel trained in the safe use of these facilities will be permitted to undertake the storage of samples received.

All biological fluids or cells/tissue suspended in fluid which requires disposal will be treated with 10% distel for 24 hours before disposal down laboratory drain. All laboratory equipment used will undergo de-sterilisation by autoclaving or, if disposable, placed in clinical waste bags for appropriate disposal.

We do not expect to have sample left over, but if there is, this will be transferred to the Digestive Diseases Tissue Bank

16. Interventions and tools

16.1 Devices

Fibroscan – transient elastography device. Manufactured by Echosens

Operated by individuals who have completed the certified training provided by manufacturer.

Owned by Site: who has responsibility for appropriate device maintenance under contract with Echosens.

16.2 Techniques and interventions

Percutaneous liver biopsy – performed under ultrasound guidance as per Barts Health standard operating procedures

Intra-operative tissue sample collection. Under direct vision of operating surgeon with biopsy equipment with ability to achieve post biopsy haemostasis utilising diathermy electrocoagulation.

16.3 Tools

Patient Questionnaires

Short Form (36) Health Survey (SF-36), measure of self-reported health status

17. Safety reporting

17.1 Adverse Events (AEs)

An AE is any untoward medical occurrence in a participant to whom an intervention has been administered, including occurrences which are not necessarily caused by or related to that intervention. An AE can therefore be any unfavourable or unintended sign (including an abnormal laboratory finding), symptom or disease temporally associated with study activities.

17.2 Adverse Reaction (ARs)

An AR is any untoward and unintended response in a participant to an intervention. All adverse events judged by either the reporting investigator or the sponsor as having a reasonable causal relationship to the intervention qualify as adverse reactions. The expression 'reasonable causal relationship' means in general that there is evidence or an argument to suggest a causal relationship.

17.3 Notification and reporting of Adverse Events and Reactions

If the AE is not defined as serious, the AE will be recorded in the study documents and the participant followed up by the research team. The AE will be documented in the participants' source documents, the Case Report Form (CRF), and, where appropriate, medical records.

17.4 Serious Adverse Events (SAEs) or reactions

A serious adverse event (SAE) is defined as an untoward occurrence that:

- Results in death,
- Is life-threatening,
- Requires hospitalisation or prolongation of existing hospitalisation,
- Results in persistent or significant disability or incapacity,
- Consists of a congenital anomaly or birth defect, or
- Is otherwise considered medically significant by the investigator.

SARs will be reported to the REC where in the opinion of the Chief Investigator the event was serious and:

- Related (it may have resulted from administration of any of the research interventions), and
- Unexpected (the type of event is not listed in the protocol or other Reference Safety Information as an expected occurrence).

17.5 Notification and reporting of Serious Adverse Events

Serious Adverse Events (SAEs) that are considered to be 'related' and 'unexpected' will be reported to the sponsor within 24 hours of learning of the event, and to the REC within 15 days in line with the required timeframe. Host sites will report SAEs to the CI via NHS email or direct telephone contact to ensure data security. The SAE may be reported to the PI at local sites who will directly notify the CI within the 24 hour timeframe.

17.6 Urgent Safety Measures

The CI will take urgent safety measures if necessary to ensure the safety and protection of the clinical study participant from immediate hazards to their health and safety. The measures will be taken immediately. The approval of the REC prior to implementing urgent safety measures is not required. However the CI will inform the sponsor and Research Ethics Committee (via telephone) of this event immediately.

The CI will inform the REC in writing within 3 days, in the form of a substantial amendment. The sponsor (Joint Research Management Office (JRMO)) will be sent a copy of the correspondence with regards to this matter.

